## 4.5. Treatment Discontinuation

Treatment discontinuation is defined as any subject who stops receiving study treatment and does not restart within 12 weeks. Subjects who permanently discontinue (for >12 weeks) CMP-001 or nivolumab may not be re-treated with the discontinued study treatment in this study. When nivolumab is permanently discontinued due to an immune related AE, CMP-001 must also be permanently discontinued.

Treatment with study treatment should continue until one of the following occurs:

- Unacceptable AE that precludes further study treatment
- 2 years of study treatment
- PD per RECIST v1.1; continuation of treatment through suspected pseudoprogression is permitted at the Investigator's discretion until confirmed PD per iRECIST
- Upon request of the Sponsor or regulatory agency
- Clinical disease progression in the opinion of the Investigator
- If medically necessary in the opinion of the Investigator
- Subject withdraws consent for study treatment
- Subject has received study treatment for 2 years
- Subject becomes pregnant or begins breastfeeding

- Subject is lost to follow-up
- Death
- End of Clinical Trial

If a subject achieves and maintains a confirmed CR or iCR by Investigator assessment, IT or SC injections of CMP-001 or the combination of CMP-001 and nivolumab may be discontinued at the Investigator's discretion once the subject meets both of the following criteria:

- Subject has been treated for at least 48 weeks (the maximum duration of study treatment is 2 years)
- Subject has received at least 3 doses of assigned treatment beyond the date of the initial CR/iCR

Subjects with PD per RECIST v1.1 as determined by Investigator assessment should remain on treatment and have a follow-up scan performed at least 4 weeks after the initial date of PD to confirm progression per RECIST v1.1 by BICR.

Subjects who discontinue study treatment should complete an EOT visit and 100-day safety follow-up contact, which should occur 100 days (+7) after the EOT or until an alternative cancer treatment is initiated, whichever occurs first (Table 1). Subjects who discontinue study treatment for reasons other than disease progression (either per RECIST v1.1 or iRECIST by Investigator assessment) should remain on study for PTFU (Section 7.6) and receive disease assessments according to the Schedule of Assessments (Table 1).

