Immune Objective Response Rate (iORR). iORR is defined as the proportion of subjects with an immune best overall response (iBOR) of confirmed immune complete response (iCR) or confirmed immune partial response (iPR) based on immunotherapy Response Evaluation Criteria in Solid Tumors (iRECIST) by Investigator assessment.

Subjects who continue study treatment beyond PD per RECIST v1.1 will be assessed by the Investigator according to iRECIST. Subjects with an iCR or iPR per iRECIST must have a confirmatory assessment performed at least 4 weeks after the initial assessment where response was declared by the Investigator and all scans should be performed at least 2 weeks after the previous CMP-001 IT injection to prevent injection-related pseudoprogression.

The confirmed iORR will be calculated as the number of subjects with a confirmed iCR or iPR divided by the number of subjects in the analysis population [iORR = (confirmed iCR + confirmed iPR)/number of subjects] for each treatment arm of the ITT Analysis Set. The two-sided 95% Clopper-Pearson CIs will be calculated for the iORR.

The immune best overall response (iBOR) will be derived as below:

If assessments are not performed or cannot be assessed following iUPD, and there is no subsequent iCPD, iSD, iPR or iCR, iUPD will continue to be used and the subject will be censored at the date of iUPD.

Immune Duration of Response (iDOR). iDOR is defined as the time from the date of the first immune response (iCR or iPR) to the date of immune confirmed progressive disease (iCPD) based on iRECIST by Investigator assessment.

iDOR is only defined for subjects who have a confirmed iBOR of iCR or iPR. The first date on which an iCR or iPR response is noted will be used to calculate iDOR, rather than the date of the confirmatory tumor assessment. Subjects who do not develop iCPD or death will be censored at the date of their last disease assessment.

Immune Progression-Free Survival (iPFS). iPFS is defined as the time from the date of randomization to date of iCPD based on iRECIST by Investigator assessment or death from any cause, whichever occurs first.

Table 1: Censoring Rules for the PFS/DOR/iPFS/iDOR

Situation	Outcome	Date	Event Description/ Censoring Reason	PFS/ DOR	iPFS/ iDOR
PD per RECIST v1.1 on/before new anticancer therapy or data cutoff date	Event	Earliest date of tumor assessment documenting PD	PD per RECIST v1.1	X	

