Death without PD per RECIST v1.1 and not receiving new anticancer therapy on/before data cutoff date	Event	Date of death	Death without PD per RECIST v1.1	X	
iCPD per iRECIST between scheduled disease assessments on/before new anticancer therapy or data cutoff date, whichever is earlier	Event	Earliest date of tumor assessment documenting iUPD	iCPD per iRECIST		X
Death without iCPD per iRECIST and not receiving new anticancer therapy on/before data cutoff date	Event	Date of death	Death without iCPD per iRECIST		X

Regeneron Pharmaceuticals Inc. / Protocol: CMP-001-011 IQVIA Biotech (Confidential) Project # SZA58924

Subjects with no post- baseline disease assessments	Censored	First Dose Date	No Adequate Disease Assessment per RECIST v1.1	PFS Only	
No PD per RECIST v1.1 or death as of data cutoff date and subject not received new anticancer therapy or received it after the data cutoff date	Censored	Date of last disease assessment on/before data cutoff date	Alive without Documented PD	X	
No PD per RECIST v1.1 or death as of data cutoff date and new anticancer therapy started before the data cutoff date	Censored	Date of last disease assessment prior to new anticancer therapy	Subsequent Anti- cancer Therapy without Documented PD	X	
PD per RECIST v1.1 or death after new anticancer therapy and the new anticancer started before data cutoff date	Censored	Date of last disease assessment prior to new anticancer therapy	Documented PD or Death after Subsequent Anti- cancer Therapy	X	
PD per RECIST v1.1 or death after new anticancer therapy and the new anticancer started after data cutoff date	Censored	Date of last disease assessment on/before data cutoff date	Documented PD or Death after Subsequent Anti- cancer Therapy	X	
PD per RECIST v1.1 or death immediately following two or more consecutive disease assessments since the last adequate disease assessment	Censored	Date of last adequate tumor assessment prior to the first missed assessment	PD or Death after Missing >= 2 Consecutive Disease Assessments	X	
Discontinuation from study before PD per RECIST v1.1 and death	Censored	Date of last adequate disease assessment	Discontinued from Study without Documented PD or Death	X	
iUPD per iRECIST at the time of PD per RECIST v1.1, continued study treatment without further tumor assessments as of data cutoff date	Censored	Date of the last tumor assessment on/before data cutoff date	No Adequate Disease Assessment per iRECIST		iPFS Only

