Regeneron Pharmaceuticals Inc. / Protocol: CMP-001-011 IQVIA Biotech (Confidential) Project # SZA58924

iUPD per iRECIST, continued study treatment with subsequent disease assessments but no confirmed PD (i.e., iCPD not assigned) or death as of data cutoff date and subject not received new anticancer therapy or received it after the data cutoff date	Censored	Date of the last tumor assessment as of data cutoff date	Alive without Documented iCPD	X
iUPD per iRECIST, continued study treatment, but started a new anti- cancer therapy before data cutoff date without evidence of iCPD or death	Censored	Date of the last tumor assessment prior to new anti- cancer therapy	Subsequent Anti- cancer Therapy without Documented iCPD	X
iCPD per iRECIST or death after new anticancer therapy and the new anticancer started before data cutoff date	Censored	Date of last disease assessment prior to new anticancer therapy	iCPD or Death after Subsequent Anti-cancer Therapy	X
iCPD per iRECIST or death after new anticancer therapy and the new anticancer started after data cutoff date	Censored	Date of last disease assessment on/before data cutoff date	iCPD or Death after Subsequent Anti-cancer Therapy	X
iUPD per iRECIST, continued study treatment, iCPD or death immediately following two or more consecutive disease assessments since the last adequate disease assessment	Censored	Date of last adequate tumor assessment prior to the first missed assessment	iCPD or Death after Missing >= 2 Consecutive Disease Assessments	X
Discontinuation from study before iCPD per iRECIST and death	Censored	Date of last adequate disease assessment	Discontinued from Study without Documented iCPD or Death	X

Situation	Outcome	Date	Event Description/ Censoring Reason	os
Death on/before data cutoff date	Event	Date of death	Death	X

Alive with study completed before data cutoff date	Censored	Study completion date	Alive on or before study completion date	X
Alive or death after data cutoff date with study continuing on/till after data cutoff date	Censored	Data cutoff date	Alive on or before data cutoff date	X
Lost to follow-up prior to data cutoff date	Censored	Last known alive date	Discontinued from study	X
Discontinued study without death and not lost to follow-up on/prior to data cutoff date	Censored	Date of study discontinuation	Discontinued from study	X

Table 2: Last Known Alive Date for the Overall Survival

Source Data	Conditions

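### The SAP dates a confirmed iRECIST progression as an event at the iUPD scan but censors the same progression on the same date if no evaluable scan follows, which biases iPFS and iDOR upward

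*SAP*

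**What the plan says.** **Event definition.** SAP Section VIII.A runs iPFS from randomization to the "date of iCPD based on iRECIST by Investigator assessment or death from any cause, whichever occurs first". For iDOR it says: "Subjects who do not develop iCPD or death will be censored at the date of their last disease assessment".

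**No scan after iUPD.** The text under iORR/iBOR in the same section reads: "If assessments are not performed or cannot be assessed following iUPD, and there is no subsequent iCPD, iSD, iPR or iCR", then "iUPD will continue to be used and the subject will be censored at the date of iUPD". It is not limited to subjects still on treatment.

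**SAP Table 1.**
- A confirmed iCPD is an event dated at the "Earliest date of tumor assessment documenting iUPD".
- The four censoring rows that begin with iUPD all describe subjects who continued study treatment. The one nearest this case is "iUPD per iRECIST at the time of PD per RECIST v1.1, continued study treatment without further tumor assessments as of data cutoff date", marked for iPFS only.
- Leaving the study before iCPD or death is censored at the last adequate assessment.
- Death without iCPD is an event at the death date, provided no new anticancer therapy was given. The row "iCPD per iRECIST or death after new anticancer therapy and the new anticancer started before data cutoff date" is censored.

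**Who is rescanned.** Protocol 4.5 lists RECIST v1.1 progression as a reason to stop treatment and leaves continuation through suspected pseudoprogression to the investigator. It says that subjects who stop "for reasons other than disease progression (either per RECIST v1.1 or iRECIST by Investigator assessment) should remain on study for PTFU". Section 7.6 ends post-treatment scans at progression. Against this, another sentence of 4.5, together with Sections 3.1 and 7.2.3.1, asks for a follow-up scan at least 4 weeks after first progression. Footnote c of the Schedule of Assessments gives 3-monthly disease assessments to subjects who are off treatment but still on study.

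**The concern.** iCPD needs an assessment after iUPD. A subject who stops at first progression and is not rescanned cannot reach iCPD, so that progression never becomes an event. The subject is censored at the moment of failing, which is informative censoring and breaks the Kaplan-Meier assumption.

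Whether the progression counts then depends on a decision to continue and rescan, made by an investigator who knows the arm. Protocol 7.2.3 warns that injected tumors may enlarge transiently, and only Arm A is injected, so that decision could differ by arm. SAP VIII.C reports iPFS and iDOR medians and 6- and 12-month rates by arm. Part of any difference could therefore reflect rescanning habits.

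**Working it through.** The plan gives no target or expected value for iPFS or iDOR, so there is no stated figure to reproduce. The check has three parts.

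**1. The rules side by side, for the same iUPD scan on the same date**

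| What follows the iUPD scan | iPFS status | Date |
|---|---|---|
| A later scan confirms progression, before any new therapy | Event | iUPD scan |
| Stops for progression, no later scan, alive | Censored | iUPD scan |
| Stops, no later scan, new therapy, then dies | Censored | Last assessment before new therapy, i.e. the iUPD scan |
| Stops, no later scan, no new therapy, then dies | Event under the Table 1 death row; censored under the text | Death, or iUPD scan |

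The first two rows differ only in whether a scan was done. In the last row two rules collide, and the SAP does not say which governs. For iDOR the same pattern applies to confirmed immune responders, through the iDOR sentence and the study-discontinuation row.

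**2. Direction**

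An event at time t with n at risk multiplies the Kaplan-Meier curve by (n−1)/n. Censoring at t multiplies it by 1 and leaves every later risk set unchanged. The curve can therefore only rise. The arms have 9 and 11 subjects (SAP II.C). One reclassified progression with the whole arm at risk raises the rest of the curve by a factor of 9/8 = 1.125 in Arm A or 11/10 = 1.10 in Arm B. If a later death counts instead, the event moves from the iUPD date to the death date, so the quantity estimated is a longer time.

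**3. Size, as illustration only**

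Inputs:
- Median m = 6.9 months, the upper end of the 4.1 to 6.9 month single-agent range in Protocol 1.1.
- Share q of first progressions with no later evaluable scan. The documents do not give it; it is assumed.
- Exponential times, q independent of time, no deaths.

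The event hazard becomes (1−q) times the true hazard. Kaplan-Meier then estimates S(t)^(1−q), and the apparent median is m/(1−q).

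| q | Median, m = 6.9 | 6-month rate | 12-month rate | Median, m = 4.1 |
|---|---|---|---|---|
| 0 | 6.9 | 54.7% | 30.0% | 4.1 |
| 0.10 | 6.9/0.90 = 7.7 | 58.1% | 33.8% | 4.6 |
| 0.25 | 6.9/0.75 = 9.2 | 63.6% | 40.5% | 5.5 |
| 0.50 | 6.9/0.50 = 13.8 | 74.0% | 54.7% | 8.2 |

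The rates are for m = 6.9. A simulation with 9 and 11 subjects, a 24-month cutoff and 10,000 runs agrees. The typical median is 9.3 months at q = 0.25, and 13.8 (n = 9) or 13.9 (n = 11) at q = 0.50. At q = 0.50 the median is not reached in 20.9% and 19.1% of runs, against 0.0% at q = 0.

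**The case against.** **Rescanning may be the norm.** Several protocol passages ask for a follow-up scan after first progression, and footnote c continues scans off treatment. Progression is not a reason to leave the study under Protocol 4.6. This stands. A reader might infer that most subjects who stop at first progression have no later scan. The documents conflict and do not support that, so the frequency is unknown.

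**iRECIST may not apply to these subjects.** The Protocol Synopsis, Protocol 7.2.3.1 and SAP VIII.A tie iRECIST to subjects treated beyond progression. That would explain the wording of the Table 1 rows and would leave a subject who stops with no recorded iUPD. Protocol 7.2 says that all assessments are read by iRECIST. On either reading the subject is in the ITT set used for iPFS and has no iCPD, so the progression is not an event. The objection changes the fix, which must also cover a missing iRECIST reading.

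**The sentence sits under iBOR.** Its derivation table is not visible in the text available. But a best response cannot be censored, so the sentence only has meaning for the time-to-event endpoints, and the event definitions lead to the same result without it.

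**iUPD is not proven progression.** True. Some unconfirmed cases may be pseudoprogression, and counting them as events is the conservative choice.

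**Impact is small.** iPFS and iDOR are exploratory and descriptive, and are not in the ad-hoc efficacy list (SAP VI.G). RECIST PFS and DOR, by BICR and by investigator, already count first progression. Reasons for censoring and the number treated beyond progression are tabulated. This stands and limits the severity.

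**Conclusion.** The point holds. The SAP's own rules give opposite outcomes to identical first progressions, depending on whether a scan followed. The bias in iPFS and iDOR is upward whether or not an iUPD was recorded for a subject who stops at RECIST progression.

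The size is not known. The figures of 9.2 and 13.8 months rest on an assumed q, an exponential model and no deaths. They concern iPFS only; for iDOR the rule reaches only confirmed immune responders, and no figure is offered.

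Three stronger readings are not supported:
- That such a subject can never be an event. Table 1 counts a later death if no new anticancer therapy was given, though at a later date.
- That the median would never be reached. That needs every first progression to go unscanned and nobody to die.
- That the rule would produce a spurious hazard ratio between arms. The SAP plans only Kaplan-Meier summaries by arm for these endpoints.

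Severity is low to moderate: descriptive secondary endpoints, 20 subjects, with ORR and RECIST PFS and DOR untouched.

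**What to change.** 1. **Add an event row to SAP Table 1 for iPFS and iDOR:** iUPD (or investigator RECIST v1.1 progression if no iRECIST reading was recorded) with no later evaluable disease assessment, where study treatment was stopped for RECIST or clinical progression, or new anticancer therapy was started. Outcome: event, dated at the iUPD or PD scan. Align the iPFS and iDOR definitions in SAP IV.B and VIII.A.
2. **Remove the overlaps.** Limit the new-anticancer-therapy rows for iPFS/iDOR to cases where an evaluable assessment after iUPD did not confirm progression. State that the new row takes precedence over the later-death and study-discontinuation rows.
3. **Narrow the censoring sentence** to subjects without a later evaluable scan who are either still on treatment with confirmation pending at the cutoff, or stopped for a reason other than progression and have started no new therapy. Say for them whether the death row overrides the censoring.
4. **Report by arm** the number of iUPDs without a later evaluable scan, and show the SAP's present rule as a sensitivity analysis.
5. **Reconcile** Protocol 3.1, 4.5, 7.2.3.1, 7.6 and Schedule footnote c on scans after stopping for progression, and Protocol 7.2 with 7.2.3.1 on who is read by iRECIST. No view is taken here on which should stand.

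The SAP cost is one table row and a few sentences, using discontinuation reasons, new-therapy dates and assessment data already planned. The downside is shorter reported iPFS and iDOR, with some pseudoprogression possibly counted as events; the sensitivity analysis shows how much that matters.
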